10.3.5. Statistical Analysis of Secondary Endpoint(s)

Tables of the secondary endpoints—device related death at 30 days, procedural related death at 30 days, procedural related SAE at 30 days, device patency at 30 days and on yearly basis, device-related SAEs, device-related death, loss of device integrity and limb salvage at yearly basis will be reported. Data will be presented descriptively with confidence intervals, where appropriate.

Missing data at the time of analysis will not be included in the denominator.

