2.1.2 Secondary Endpoint(s)

Selected events that are illustrative of the device's potential impact to a patient from a safety perspective, overall device function described as patency or device durability captured as device integrity are to be as the registry's secondary endpoints. Possible endpoint events will be identified from site reports with some secondary endpoints within scope of CEC adjudication.

The secondary endpoints for the VBX 17-04 registry are the following:

- VBX Stent Graft-related death within 30 days post-treatment
- Procedural-related death within 30 days post-treatment
- Procedural-related SAE within 30 days post-treatment
- VBX Stent Graft patency (primary, primary assisted, secondary) through 30 days post-treatment
- VBX Stent Graft patency (primary, primary assisted, secondary) through five years post-treatment
- VBX Stent Graft-related SAE through five years post-treatment
- VBX Stent Graft-related death through five years post-treatment
- Loss of device integrity through five years post-treatment
- Limb salvage through five years post-treatment

Protocol Term	Definition			
Procedural Success	Technical Success (successful access, delivery, accurate deployment, and withdrawal of catheters) with patent VBX Stent Graft at end of procedure			
Patency	 Primary - Uninterrupted patency with no procedures performed on or at the margins of the treated segment. Primary Assisted - Any procedure performed in the treated segment before thrombosis that might prevent eventual failure. Secondary - Any procedure that restores patency after thrombosis. 			
Loss of Device Integrity	 Defined as any of the following: Device damage that compromises device functionality (stent fractures, graft tears, cuts, holes, delamination) Transient (compression) or permanent stent-graft collapse (invagination) following complete device deployment, resulting in an overall reduction in the vessel luminal diameter 			
Limb Salvage	Freedom from Major Tissue Loss—extending above transmetatarsal level; functional foot no longer salvageable ²⁸			
Reintervention	An additional unanticipated interventional or surgical procedure (including conversion to open surgery), related to the device (including withdrawal of the delivery system) or procedure. Anticipated or unanticipated status will be determined at the discretion of the investigator			

Table 1. Protocol Definitions

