Analysis of the secondary endpoints—device related death at 30 days, procedural related death at 30 days, procedural related SAE at 30 days, device patency at 30 days, in addition, device patency, device-related SAEs, device related deaths and loss of device integrity will be reported yearly as both yearly percentages and rates. Data will be presented descriptively with 95% confidence intervals, where appropriate. Subjects with missing information on these outcomes will not be included in the analysis.

vi) Analysis by Treatment Category

Individual device treatment indications will be categorized into larger groups "Treatment Categories" based upon either similar device function or purpose. Combining treatment indications into larger groups will permit the analysis of general treatment concepts where an analysis based upon an individual indication would not be feasible. Analyses of a Treatment Category will be performed descriptively with no pre-determined hypothesis.

vii) Analysis of Individual Treatment Indications

At the conclusion of enrollment, an evaluation of the distribution of device use across individual pathologies will be performed. If feasible, device experience by indication will be tabulated for descriptive analysis.

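### Five-year patency and device integrity are to be reported as complete-case yearly percentages, so the later-year figures can be biased up or down depending on a denominator rule that the visible plan does not state.

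*SAP*

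**What the plan says.** - **Endpoints.** SAP 2.1.2 lists "VBX Stent Graft patency (primary, primary assisted, secondary) through five years post-treatment", and likewise device-related SAE, device-related death, loss of device integrity and "Limb salvage through five years post-treatment". The wording is cumulative.
- **Reporting.** In SAP 6.0 v, patency, device-related SAEs, device-related deaths and loss of integrity "will be reported yearly as both yearly percentages and rates". The term *rates* is not defined.
- **Missing data.** SAP 6.0 v: "Subjects with missing information on these outcomes will not be included in the analysis". Protocol 10.3.5: "Missing data at the time of analysis will not be included in the denominator".
- **Definitions.** Primary patency is "Uninterrupted patency with no procedures performed on or at the margins of the treated segment". Secondary patency is "Any procedure that restores patency after thrombosis", which describes a procedure and not the point at which secondary patency is lost. None of the three patency definitions mentions explant or bypass.
- **Withdrawal.** Protocol 5.9 lists explant, and a graft that cannot be evaluated (a bypassed graft is its example), among the grounds on which a patient may be withdrawn. Data from before withdrawal are kept and used as appropriate.
- **Follow-up.** Protocol 5.8 leaves the frequency and type of imaging to the follow-up physician and accepts a phone contact as a visit in some cases.
- **Limb salvage.** Protocol 10.3.5 promises it yearly ("loss of device integrity and limb salvage at yearly basis will be reported"). The analysis list in SAP 6.0 v omits it.

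**The concern.** A percentage that is cumulative over five years needs a rule for patients whose follow-up stops early. The visible plan has only an exclusion rule. Two of the listed withdrawal grounds, explant and bypass, may themselves follow from graft failure, so the exclusion can be related to the outcome. Discretionary imaging and phone visits mean that patency can also be missing for patients still in the registry.

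Two readings fit the text:

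- **First reading.** The year-5 percentage uses only patients evaluated at year 5. Failures withdrawn earlier leave the denominator, and patency is biased upward.
- **Second reading.** A known failure is not missing, so it stays. Patients who left event-free are missing and are dropped. Failures accumulate while event-free patients do not, and patency is biased downward.

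Estimating device performance is the purpose of this registry, so the long-term patency figure would rest on an analysis choice not fixed in advance.

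**Working it through.** **The plan's own figure.** The documents give no five-year patency, attrition or explant rate, so there is no long-term figure to reproduce. The one precision statement, a margin of error below 6% with 280 patients, is reproduced by the worst-case normal approximation: 1.96 × √(0.5 × 0.5/280) = 5.86%. It describes sampling error at full n and does not cover denominator bias.

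**Inputs.** From the documents: 280 implanted patients, five years, exclusion of missing outcomes, 95% intervals. My assumptions: failure f = 3% per year (range 1% to 5%); other loss c = 5% per year, independent of outcome; share of failures that are withdrawn w = 0, 10%, 25%, 50%.

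**Truth.** S = (1 - f)^5 = 0.97^5 = 0.8587.

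**First reading.** Independent loss cancels, leaving A = S / [S + (1 - S)(1 - w)].
- w = 0: A = S, no bias.
- w = 10%: 0.8587 / (0.8587 + 0.1413 × 0.90) = 0.8587/0.9859 = 0.871.
- w = 25%: 0.8587/0.9647 = 0.890.
- w = 50%: 0.8587/0.9294 = 0.924.

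Evaluable n = 280 × 0.95^5 × [S + (1 - S)(1 - w)] = 216.7 × 0.9859, 0.9647 or 0.9294 = 214, 209 or 201.

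**Second reading.** With hazards h = -ln 0.97 = 0.03046 and g = -ln 0.95 = 0.05129:
- Event-free and still followed: E = exp(-5 × 0.08175) = 0.6645.
- Observed failures: F = (0.03046/0.08175) × (1 - 0.6645) = 0.1250.
- B = E/(E + F) = 0.6645/0.7895 = 0.842, with n = 280 × 0.7895 = 221.

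**Results at 3% per year (truth 85.9%)**

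| Reading | Estimate | Bias (points) | Exact 95% CI | Includes truth |
|---|---|---|---|---|
| First, w = 10% | 87.1% | +1.2 | 81.6 to 91.1% | yes |
| First, w = 25% | 89.0% | +3.1 | 83.9 to 92.9% | yes |
| First, w = 50% | 92.4% | +6.5 | 88.0 to 95.8% | no |
| Second | 84.2% | -1.7 | 78.7 to 88.7% | yes |

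**Range over f.** At 1% per year (truth 95.1%), the first reading is off by +0.5, +1.2 and +2.4 points at w = 10%, 25% and 50%, and the second by -0.7. At 5% per year (truth 77.4%), the figures are +1.8, +4.6 and +9.9, and -2.5.

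**Outcome-related imaging.** Suppose true patency is 85%, nobody is withdrawn, and 60% of patent but 95% of failed grafts are imaged. The complete-case value is 0.85 × 0.60 / (0.85 × 0.60 + 0.15 × 0.95) = 0.510/0.6525 = 78.2%.

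**Is Kaplan-Meier alone enough?** No. If withdrawn failures are censored like other leavers, it estimates exp[-5h(1 - w)] = 87.2%, 89.2% and 92.7% at w = 10%, 25% and 50%. With those failures counted on their date it returns 85.9%. In a simulation of 1,000,000 patients with other failures detected only at annual evaluations and censoring at the last one, it gave 85.9%, 85.8% and 85.7%.

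**The case against.** The strongest reply is that the first reading is strained. A recorded explant or bypass is known information, not missing information. Protocol 5.7 asks for reinterventions to be recorded, Protocol 5.9 keeps data from before withdrawal, and both documents include all eligible treated patients in the secondary analyses. The primary patency definition already points towards failure once the treated segment has a procedure. Withdrawal under 5.9 is also optional. This largely stands for primary patency, where an ordinary reintervention is not a withdrawal ground and a high w is hard to justify. It does not remove the problem: keeping known failures while dropping event-free losses is the second reading, which errs downward.

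The second reply is that the rule may sit in text not shown. Protocol 5.12 and 10.1, the visit-window table, part of SAP 4.0, and SAP 7.0 and 9.0 carry little or no text in this copy, and *rates* could mean a time-based estimate. That limits the point to the visible text. The exclusion sentences are visible, though, and would still have to be reconciled with any such rule.

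A reader might infer three stronger things that the documents do not support:
- That the plan removes explanted or bypassed patients as missing, so that patency will be overstated. The text permits this but does not say it.
- That the distance between the readings (92.4 - 84.2 = 8.2 points at w = 50%) is the bias. It compares two biased values; neither is that far from the truth.
- That every explant or bypass is a failure under all three patency types. The definitions do not say so, and a patent graft may be explanted.

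**Conclusion.** The point holds for the visible text. Complete-case yearly percentages do not suit endpoints defined through five years when failure can lead to withdrawal and imaging is discretionary. The direction of bias depends on an unstated denominator rule.

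At an assumed 3% failure and 5% independent loss per year, the bias is +1.2 to +3.1 points with 10% to 25% of failures withdrawn, +6.5 with 50%, and -1.7 on the second reading. In all but the 50% case the exact interval still covers the truth. There is no upward bias if no failures are withdrawn and other loss is independent. All of these rates are assumptions, and one failure rate stands in for all three patency types. No size was worked out for device integrity, SAE, death or limb salvage.

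The consequence is limited to descriptive secondary estimates with no hypothesis test. The 30-day primary endpoint is not affected. It should be fixed because a better method is standard and inexpensive, not because the registry's main result is at risk.

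**What to change.** In SAP 6.0 v now, and in Protocol 10.3.5 at the next amendment:

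1. Replace the complete-case yearly percentages for patency and device integrity with Kaplan-Meier estimates and 95% CIs at 30 days and 1 to 5 years. Censor event-free patients at their last device evaluation and report numbers at risk.
2. State that an endpoint failure documented at or before withdrawal, including loss of patency or integrity leading to explant or bypass, counts as a failure on its date and is neither missing nor ordinarily censored.
3. For explant or bypass with the graft documented patent or of unknown status, state the classification under each patency type and show the alternative as a sensitivity analysis. The unknown category is needed because Protocol 5.9 only recommends an evaluation before withdrawal, where possible.
4. For device-related SAE, device-related death and limb salvage, use a time-to-event estimate censored at last contact instead of dropping incomplete subjects. Treating death from other causes as a competing event is optional.
5. Define *rates*, and add limb salvage to the SAP analysis list to match the protocol.
6. If text not visible in this copy already covers this, cross-refer to it and remove the conflicting exclusion sentences.

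The cost is SAP wording and standard survival code. The protocol change needs ethics committee approval under Protocol 6.4, which is why it can wait for the next amendment. The downsides are slightly more analysis work and possibly less favourable reported patency. Kaplan-Meier still assumes independent loss and reasonably regular evaluation; outcome-related imaging would remain a limitation to report.

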### 5.9. Patient Withdrawal from the Registry

An implanted patient may withdraw from the registry at any time and should notify their follow-up physician in this circumstance. The investigator may also withdraw the patient from the registry at any time based on his / her medical judgment. When withdrawing the participation of a patient for any reason, the site investigator or sub-investigator records the date of discontinuation, the reason for discontinuation, and the patient's condition at the time of discontinuation on the eCRF. Patients may be considered withdrawn for any of the following:

- The VBX Stent Graft is explanted
- Death
- Voluntary withdrawal
- Investigator withdrawal

• Any other medical condition where evaluation of the VBX Stent Graft is not feasible (*e.g.*, bypassed VBX Stent Graft)

If the discontinuation is caused by the development or worsening of AEs, information on the AEs must also be recorded on the appropriate eCRF. All data generated prior to patient withdrawal will be maintained, and study data will be used as appropriate. If such withdrawal is due to problems related to the registry device safety or performance, the investigator shall ask for the patient's permission to follow his / her status / condition outside the registry

If possible, an additional evaluation of the VBX Stent Graft(s) is recommended prior to their withdrawal from the registry.

Sites are advised to provide patients with a recommendation on the long-term care and follow-up necessary for a device used in their specific pathology.

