5.11. Registry Participant Completion

An implanted patient has completed the registry once an element of the last requested follow-up visit has been performed or the collection of follow-up information would be outside of the visit windows. An implanted patient that does not complete these requirements due to voluntary withdrawal, physician withdrawal, death, or any other reason will be considered a withdrawal. Regular follow-up after registry completion is suggested to be conducted in accordance with the discretion of the site investigator or sub-investigator(s) and standard of care.

Patients will not be provided with any medical care by Gore after registry completion or withdrawal.

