9.1.5. Patient Death

In this clinical investigation, death is not considered an AE, but rather the outcome of an AE. Any ongoing / unresolved AEs will be considered as ongoing at the time of death or registry withdrawal. An effort must be made to collect source documentation or death certificate in the case of death.

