5.0 Clinical Event Committee

An independent Clinical Event Committee (CEC) will review safety- related, clinical events during the study to ensure the consistency of endpoints reported by the site. The VBX 17-04 CEC will be comprised of an interdisciplinary team of three members with pertinent expertise who are not directly involved in the conduct of the study.

The scope of the CEC activity includes the following:

- 1. General review and adjudication of Serious Adverse Events (SAEs) to include:
 - a. Adjudication on the SAE designation
 - b. Adjudication of the relationship of the SAE to the study device, procedure, or unrelated
- 2. Protocol Deviation review (as appropriate)
 - a. Due to the potential safety concern, protocol deviations associated with inclusion/exclusion criteria will be reviewed and the CEC will assess their risk for significant medical events that would not be expected from a subject that met all inclusion/exclusion criteria.

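### The complete-case rule for device-related death and SAE through five years does not estimate the risk in treated patients, and no rule covers deaths from other causes

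*SAP*

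**What the plan says.** Two long-term safety endpoints are concerned. SAP 2.1.2 lists "VBX Stent Graft-related death through five years post-treatment" and, over the same horizon, device-related SAE. Protocol 3.2.3 has the same list.

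SAP 6.0 v says that these outcomes "will be reported yearly as both yearly percentages and rates", with 95% confidence intervals where appropriate. On incomplete outcomes it says "Subjects with missing information on these outcomes will not be included in the analysis". Protocol 10.3.5 says "Missing data at the time of analysis will not be included in the denominator". Neither document defines missing information.

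On early exits, Protocol 5.9 lists explant, death, voluntary withdrawal, investigator withdrawal and conditions that prevent evaluation of the graft. Protocol 5.11 adds that a patient who does not complete "due to voluntary withdrawal, physician withdrawal, death, or any other reason will be considered a withdrawal". Protocol 5.9 also says "All data generated prior to patient withdrawal will be maintained, and study data will be used as appropriate".

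On the status of a death, Protocol 9.1.5 says that "death is not considered an AE, but rather the outcome of an AE". SAP 5.0 puts within the scope of the Clinical Events Committee "Adjudication of the relationship of the SAE to the study device, procedure, or unrelated".

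**The concern.** Someone who dies of an unrelated cause in year 2 cannot later have a device-related death or SAE. That death is a competing event. It is neither a gap in the data nor grounds for removing the patient. A patient lost in year 2 is a different case: follow-up to that date is informative, and later status is unknown. The plan has one rule for both, exclusion when information is missing, and it does not say which patients that covers.

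A programmer could take the rule to mean that anyone without year 3 to 5 data leaves the five-year percentage, while anyone with a recorded event stays. The result is events divided by events plus event-free patients followed to five years. It would move with background mortality and loss to follow-up as well as with the device.

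Eligibility excludes only a life expectancy under 12 months (Protocol 4.3), and the treatment categories include rupture and fenestrated or branched repair (Protocol 4.1.1). Appreciable non-device mortality over five years is therefore plausible. Categories that differ in it could look different for reasons unrelated to the device. SAP 6.0 i also foresees analyses for annual reports, when many patients may not yet have reached the later years.

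**Working it through.** **The plan's own figure.** The stated precision is a margin of error below 6% with 280 patients. The Wald half-width at p = 0.5 is 1.96 × √(0.25/280) = 5.86%, so it reproduces (Wilson 5.82%; exact 6.01%, marginally above). It concerns sampling error and does not bear on the bias examined here.

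**Inputs.** n = 280 comes from the SAP sample size section. The documents give no five-year device-related event rate, non-device mortality or dropout figure. The following are assumptions: a five-year risk of 5% (14 of 280), and C, the share of treated patients who are event-free and dropped, from 10% to 40%.

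**Step 1: other-cause deaths dropped, events kept, no other loss.** The risk in treated patients is x/n = 14/280 = 5.0% (exact 95% CI 2.8% to 8.3%; binomial SE √(0.05 × 0.95/280) = 1.30 points). The complete-case figure is x/[n(1-C)], a factor of 1/(1-C).

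| C | Factor | Complete-case | Exact 95% CI | Shift in SE |
|---|---|---|---|---|
| 10% | 1.11 | 14/252 = 5.6% | 3.1% to 9.2% | 0.56/1.30 = 0.4 |
| 20% | 1.25 | 14/224 = 6.25% | 3.5% to 10.3% | 1.25/1.30 = 1.0 |
| 30% | 1.43 | 14/196 = 7.1% | 4.0% to 11.7% | 2.14/1.30 = 1.6 |
| 40% | 1.67 | 14/168 = 8.3% | 4.6% to 13.6% | 3.33/1.30 = 2.6 |

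The factor does not depend on the event rate. A risk of 2% would read 2.2% to 3.3% over the same range.

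**Step 2: other-cause deaths kept as known non-events.** The denominator stays at 280 and the figure stays at 14/280 = 5.0%. This bias is zero.

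**Step 3: patients lost alive and event-free, events kept.** Here x/n is too low, because later events go unseen, so 1/(1-C) is an upper limit for the overstatement. With constant hazards and loss unrelated to risk, the observed share F = 5% and lost share C imply a risk of 1 - exp{ln(1-F-C) × F/(F+C)}. For C = 20% this is 1 - exp(-0.2877 × 0.2) = 5.59%, against a complete-case 6.25%, a factor of 1.12. For C = 30% it is 5.97% against 7.14%, a factor of 1.20. The bias is smaller than for deaths but does not vanish, so settling the deaths alone does not repair the rule.

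**Step 4: SAE patients who later withdraw are also dropped.** Let 14 of 280 have a device-related SAE, drop 20% of the 266 event-free patients (212.8 remain), and drop a share q of the 14.

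- q = 0: 14/(14 + 212.8) = 6.2%
- q = 20%: 11.2/(11.2 + 212.8) = 5.0%
- q = 40%: 8.4/(8.4 + 212.8) = 3.8%

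The direction for SAE therefore depends on a rule that the plan does not give. This reversal cannot arise for device-related death, where the event itself ends follow-up.

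**Step 5: is Kaplan-Meier enough?** The plan does not name it. If one minus Kaplan-Meier were used with other-cause deaths censored, the formula in Step 3 gives its value: for a 5% risk, 5.6% at C = 20% and 6.0% at C = 30%. It overstates by less than the complete-case figure.

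**The case against.** A reader might infer that the plan computes five-year percentages among survivors plus events and so necessarily overstates device risk. The documents do not support that.

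- Neither document says that an unrelated death is missing information. Withdrawal in Protocol 5.9 and 5.11 is a disposition category, and data before withdrawal are kept. A death is the outcome of an AE, an AE leading to death is an SAE (Protocol 9.1.2), and the committee adjudicates its relationship. The device-related-death status of such a patient is therefore known. AEs are reported up to discontinuation (Protocol 9.1.4), so SAE status is also collected to that point.
- SAP 6.0 ii puts all eligible treated patients in the secondary analyses.
- Yearly percentages could be per interval, and rates could be per person-time, with patients contributing until death.
- Parts of the plan cannot be read in the public copy: Protocol 10.1 shows only its heading, and little of SAP 7.0 to 9.0 is visible. Denominator rules may stand there.
- The endpoints are descriptive, with no hypothesis and no pass/fail criterion.

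All of this stands, and it rules out an unconditional claim of upward bias. It does not settle the point. The exclusion rule is written down, and where follow-up is incomplete it does not yield the risk through five years even if deaths are kept (Step 3). Interval percentages and person-time rates do not by themselves give that risk either. SAP 6.0 ii and the exclusion sentence in 6.0 v are not reconciled.

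**Conclusion.** The point holds in conditional form. In the text that can be read, the only stated handling of incomplete outcomes for these two endpoints is complete-case exclusion. With incomplete follow-up, that does not estimate the five-year risk in treated patients. If event-free patients who die of other causes are dropped and events are kept, the inflation is 1/(1-C), or 1.11 to 1.67 for an assumed C of 10% to 40%. For patients lost alive, that factor is an upper limit. If unrelated deaths are kept as known non-events, their part of the bias disappears. For SAE the error can vanish or reverse if event patients who later withdraw are excluded too.

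The size rests entirely on assumed mortality, loss and event rates. The conclusion that the same data can give materially different safety percentages under readings the text allows does not depend on the particular values. This is a cheap improvement to descriptive secondary analyses, and it leaves the 30-day primary endpoint untouched.

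**What to change.** In SAP 6.0 v:

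1. Define missing information. State that an adjudicated death from another cause is a known outcome, and that an event before withdrawal is always counted.
2. Replace the complete-case five-year percentage for device-related death and device-related SAE with cumulative incidence at each year (Aalen-Johansen) and 95% confidence intervals. Treat death from other causes as a competing event, and censor only at administrative end, loss to follow-up or withdrawal of consent.
3. State how exits after explant, graft bypass or investigator withdrawal enter, since they may be linked to the device.
4. If rates are also reported, give their person-time denominator.
5. Show all-cause death beside these estimates.

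Protocol 10.3.5 should be aligned. AE onset dates and outcomes (Protocol 9.1.3) and discontinuation dates and reasons (Protocol 5.9) are already collected, so no new data are needed. The cost is SAP wording, slightly more programming and one extra column per table.
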